### 6.3 Endometrial Thinning

Endometrial thinning prior to ablation is recommended and can be achieved through medication or timing of the menstrual cycle to the early proliferative phase, per Investigator discretion.

### 6.4 Cerene Ablation Treatment

#### 6.4.1 Subject Preparation for Treatment

- Urine for pregnancy
- Confirm subject eligibility
- Uterine sound measurements
- Endometrial thickness measurement: [REDACTED]
- Administer pre-procedure medications for anesthesia and/or analgesia

#### 6.4.2 Ablation Treatment

**NOTE:** Introduction of air and/or bubbles via saline hysteroscopy immediately prior to the ablation could interfere with the subsequent ablation. Use of CO2 hysteroscopy is not indicated immediately prior to ablation. Hysteroscopy, of any kind, immediately post ablation treatment is not indicated.

- Prepare subject for ablation procedure per standard practice
- Administer local analgesics, paracervical block, and anesthesia per investigator discretion
- Record all analgesia/anesthetics administered
- Initiate the ablation treatment with the Cerene Device per the Instructions for Use and physician training materials
- Assess and record subject's pain intensity (0-10):
  1. After subject preparation and cervical dilation, but before device insertion
  2. After device insertion (before liner deployment)
  3. After liner deployment (before ablation)
  4. After 1 minute of ablation
  5. At end of ablation
  6. Post ablation: one additional pain measurement between >15 and 30 minutes, inclusive.
- Ultrasound monitoring during device placement and ablation may be used, but is not mandatory

- Dispose of Nitrous oxide per standard hospital procedure and/or according to Instructions for Use and physician training materials

#### 6.5 Post-Treatment through Discharge

- Allow the subject to recover following treatment and monitor her per standard practice
- Record medication administered post-procedure
- Record adverse events
- Assess and record subject's pain intensity at discharge/dischargeability
- Record the subject's time and date of discharge

- Record time and date the subject is eligible for discharge

#### 6.6 Day 1 Post treatment (+3 days)

- Contact subject next day after Cerene Device treatment procedure to assess status (telephone or office visit)
- Record subject's adverse events
- Assess subject's pain intensity (0-10)

#### 6.7 Week 2 Post treatment (+ 2 weeks)

- Perform pelvic exam
- Query subject on return to activities of daily living
- Record Adverse Events
- Review PBLAC diary recording and instructions. Remind subject to submit monthly PBLAC diary.
- Query subject regarding the use of additional medications or surgical procedures to manage heavy menstrual bleeding

**6.8 Month 3 Post treatment ( $\pm$  4 weeks)**

[figure not shown]
- Perform pelvic exam, if needed
- Administer MIQ and PMSIS questionnaires
- Collect and review PBLAC
- Query subject regarding the use of additional medications or surgical procedures to manage heavy menstrual bleeding
- Record Adverse Events since last follow-up

**6.9 Month 6 Post treatment ( $\pm$  4 weeks)**

- Perform pelvic exam, if needed
- Administer MIQ and PMSIS questionnaires
- Collect and Review PBLAC
- Query subject regarding the use of additional medications or surgical procedures as intervention to manage heavy menstrual bleeding
- Record Adverse Events since last follow-up

**6.10 Month 12 Post treatment ( $\pm$  4 weeks)**

- Perform pelvic exam
- Collect FSH when age is > 40 years
- Administer MIQ and PMSIS questionnaires
- Assess uterine cavity access and healing via hysteroscopy
- Collect and Review PBLAC
- Query subject regarding the use of additional medications or surgical procedures as intervention to manage heavy menstrual bleeding
- Record Subject satisfaction and recommendation
- Record Adverse Events since last follow-up

**6.11 Month 24 Post Treatment ( $\pm$  4 weeks)**

Collect the information listed below during the subject's office or telephone contact visit.

- Query the subject regarding:

1. Any medication that she is taking or any surgical procedure or other treatment that she has undergone for uterine bleeding
2. Gynecologic adverse events
3. Type of contraception, compliance with contraception, and if she is pregnant or had a pregnancy
4. Menstrual status
5. Satisfaction with the results of the Cerene treatment and willingness to recommend the procedure to a friend or relative

- Administer the MIQ and PMSIS questionnaires during the contact

#### **6.12 Month 36 Post Treatment ( $\pm$ 4 weeks) / Subject Exit**

Collect the information listed below during the subject's office or telephone contact visit.

- Query the subject regarding:
  1. Any medication that she is taking or any surgical procedure or other treatment that she has undergone for uterine bleeding
  2. Gynecologic adverse events
  3. Type of contraception, compliance with contraception, and if she is pregnant or had a pregnancy
  4. Menstrual status
  5. Satisfaction with the results of the Cerene treatment and willingness to recommend the procedure to a friend or relative
- Administer the MIQ and PMSIS questionnaires during the contact
- Exit subject at this visit per protocol

#### **7 Adverse Event Reports**

An adverse event is any sign, symptom, illness, clinically significant abnormal laboratory value, or other adverse medical event that appears or worsens in a subject during a clinical study, regardless of whether or not it is considered related to the procedure / investigational device.

Anticipated signs and symptoms (e.g. nausea, cramping) which occur in the recovery room will not be considered adverse events unless they occur with greater severity or intensity than anticipated.

It is the responsibility of the investigator to report all adverse events as required by this protocol. Adverse event information will be collected throughout the study at each subject contact as defined in the table below. Adverse events will be recorded on the Adverse Event CRF by the investigator or study coordinator and include start and stop date, anticipated or unanticipated,

outcome, severity, seriousness, and relatedness to the procedure, device, and/or pre-existing condition.

**Table 3: Adverse Event Reporting at Subject Follow-up Contacts**

Type of Adverse Event	Follow-up Visit for Subject Query / Assessment
Any non-serious AE or SAE	Any contact through the Month 12 follow-up visit
Gynecologic non-serious AE or SAE	After Month 12, any contact through subject exit
Pregnancy	Any contact through subject exit

[REDACTED]

[REDACTED]

[REDACTED]

[REDACTED]

[REDACTED]

[REDACTED]

The number and percent of subjects experiencing an adverse event will be summarized by site, severity, relatedness, and seriousness. The number and percent of subjects who withdraw or discontinue from the study due to an adverse event will also be tabulated.

Serious adverse events and unanticipated adverse device effects must be reported to the Sponsor immediately or within 24 hours (one working day) by telephone ([contact]), fax ([contact]), or e-mail ([contact]). To maintain subject confidentiality, the subject will be identified only by the subject study identification number. A written report must follow the initial notification within five working days and include a full description of the event and sequelae, in the format detailed by the serious adverse event reporting form. After the Month 12 follow-up visit, events that are not gynecologic SAEs or device related are not required to be reported. A subject's death must always be reported regardless of cause.

A serious adverse event must be followed until it has subsided or, in case of permanent impairment or residual effects, until the event stabilizes, and the overall clinical outcome has been ascertained.

**Severity of Adverse Events:** The definitions below will be used to rate the severity of adverse events for this study.

- **Mild:** Awareness of signs or symptoms, but easily tolerated and transient; causing no loss of time from normal activities; symptoms would not require medication or a medical treatment; signs and symptoms are transient.
- **Moderate:** Marked symptoms and discomfort severe enough to cause moderate interference with the subject's usual activities. Symptomatic treatment is possible.
- **Severe:** Incapacitating with inability to do work or usual activities; signs and symptoms may be of systemic nature or require medical intervention and/or treatment. Hospitalization may be required or prolonged.

**Serious Adverse Events (SAE):** An Adverse event is categorized as an SAE if it meets any of the criteria listed below. SAE categorization is independent of the severity rating applied above.

- Death
- Life-threatening: the subject was at substantial risk of dying at the time of the adverse event, or if use or continued use of the device or other medical product might have resulted in the death of the subject
- Hospitalization (initial or prolonged) due to an adverse event

Emergency room visits that do not result in admission to the hospital will be evaluated for one of the other serious outcomes (e.g., life-threatening; required intervention to prevent permanent impairment or damage; other serious medically important event).

A hospitalization or prolongation of hospitalization will not be regarded as an SAE if at least one of the following exceptions is met:

- The admission results in a hospital stay of less than 12 hours
- The admission is pre-planned (such as elective or scheduled surgery arranged prior to the start of the study)
- The admission is not associated with an AE (such as hospitalization for purposes of respite care)
- Disability or permanent damage
  - Disability means a substantial disruption of a person's ability to conduct normal life's functions
- Requires medical or surgical intervention to prevent permanent impairment of a body function or permanent damage to a body structure
- Congenital anomaly / birth defect caused by exposure to a medical product prior to conception or during pregnancy

- Any medically important serious adverse event as judged by the investigator  
This includes an adverse event that does not fit the other outcomes, but it may jeopardize the subject and may require medical or surgical intervention (treatment) to prevent one of the other outcomes. Examples include allergic bronchospasm requiring treatment in an emergency room, serious blood dyscrasias (blood disorders) or seizures/convulsions that do not result in hospitalization. The development of drug dependence or drug abuse would also be examples of important medical events.

Serious Deterioration in the State of Health, per Health Canada SOR/98-282:

- Serious Deterioration in the State of Health, as defined in the Health Canada Regulations, involves: life-threatening disease, disorder or abnormal physical state,
- The permanent impairment of a body function or permanent damage to a body structure, or
- A condition that necessitates an unexpected medical or surgical intervention to prevent such a disease, disorder or abnormal physical state or permanent impairment or damage.

**Unanticipated Adverse Device Effect (UADE):** Any serious adverse effect on health or safety or any life-threatening problem or death caused by, or associated with, a device, if that effect, problem, or death was not previously identified in nature, severity, or degree of incidence in the investigational plan or application (including a supplementary plan or application, or investigator's brochure), or any other unanticipated serious problem associated with a device that relates to the rights, safety, or welfare of subjects.

**Near incident:** Any malfunction or deterioration in the characteristics and/or performance of the device which might have led to death or serious deterioration in health; incident occurred and is such that if it occurred again, it might lead to death or serious deterioration in health.

**Adverse Event Relationship:** The relationship of an Adverse Event to a pre-existing condition, underlying disease, screening procedure, ablation procedure or treatment, or the device will be attributed as not related or related.

**Adverse Event Status (outcome):** The outcome of an adverse event should be assessed at every subject contact to determine if it has resolved or stabilized, or is ongoing. It can be updated if new information is received. The status should be recorded as follows:

- Resolved: the AE has stopped and the stop date should be recorded.  
NOTE: The severity of an AE may change. If the severity changes, the AE with the existing severity should be recorded as resolved and the stop date when the severity changed should be entered. A new AE with the updated severity should be recorded with a start date that the severity changed.
- Resolved with residual side effects: this outcome would be recorded if the AE has stabilized but a pathological or residual condition continues. Therefore, the AE

symptom(s) has not completely resolved and a new baseline for the subject/patient is established since full recovery is not expected (the AE is expected to continue for an undetermined amount of time). A stop date for the AE should be recorded as the approximate date of AE stabilization.

- Not resolved: this outcome would be recorded at subject exit if the adverse event has not stopped or stabilized. A stop date for the AE should NOT be recorded.
- Fatal: this outcome would be recorded if the subject expired. The stop date for the AE is recorded as the date of death.
- Other: this outcome would be recorded if any of the outcomes listed above do not apply. The reason for other should be specified. A stop date for the AE may or may not be recorded.

## 8 Risks and Benefits

### 8.1 Potential Risks to the Subject

Participation in this clinical study may expose the subject to potential risks associated with the device or the procedure. Safety events will be collected and reviewed throughout the study. Investigators will be notified of any additional risks identified during the study that could affect the health, safety, or welfare of the study subjects.

Risks associated with the use of the **Cerene Device** are anticipated to be similar to risks associated with other endometrial cryoablation products. The list of potential risks, provided below, is based on a review of scientific literature, animal studies, product risk and clinical risk analyses performed by the Sponsor.

- Abdominal bloating
- Abdominal pain
- Additional intervention for bleeding
- Anesthesia-related, adverse reaction or over-medication
- Cervical stenosis
- Cervical tear/injury
- Damage to adjacent organs (e.g. bowel burn or bladder injury) (Note: a severe bowel injury could potentially lead to death)
- Dysmenorrhea
- Dyspareunia
- Embolism
- Endometritis
- Fever
- Hematometra
- Infection, sepsis, or death due to sepsis
- Nausea

- Nitrous oxide impairment (dizziness)
- Pelvic cramping
- Pelvic or abdominal injury resulting from excessive uterine pressures
- Possible missed diagnosis of uterine cavity pathology post-endometrial ablation
- Post-ablation tubal sterilization syndrome
- Pregnancy (Note: Pregnancy following ablation may be life threatening to both mother and fetus)
- Urinary tract infections
- Uterine perforation
- Uterine synechiae (Asherman's syndrome)
- Vaginal bleeding
- Vaginal discharge
- Vomiting
- Some or all of these risks may require a need for reoperation or subsequent treatment and/or may lead to permanent disability or death.

Note: Vaginal discharge usually happens during the first few days following treatment and may last as long as six weeks. It is generally described as bloody during the first few days, a mixture of blood and fluid for another week, then followed by a watery discharge that can be substantial at times. This is an anticipated symptom of the cryotherapy treatment and is not considered an adverse event unless the vaginal discharge suggests infection.

There is also the possibility of an unanticipated reaction to the study device and/or medications used during the procedure that could require emergency intervention. Subjects with known sensitivity to drugs that may be used during the procedure are excluded from study participation. Should a subject experience a significant side effect for which there is concern, she will be managed per investigator standard of care and institutional requirements.

If sedation is used, potential risks from the agents and/or gases used include postoperative pain, nausea and vomiting, dizziness, drowsiness, shivering, liver toxicity, and/or cardiovascular events. Trained professionals with extensive experience and expertise who routinely administer anesthesia to subjects will be responsible for the induction and associated monitoring required for this type of procedure. Study subjects will be monitored throughout treatment, recovery, and discharge per investigator and institution requirements. In addition, the risks of blood draws include temporary pain and discomfort from the needle stick, and/or tenderness, redness or bruising at the site, bleeding, fainting and lightheadedness.

This list of risks may not be complete and it is possible that unforeseen risks could occur. There is also the risk that the procedure may not be effective or the subject may not be able to be treated because of obstructions within the cavity, an unusual cavity shape, or inadequate uterine dimensions that are determined at completion of screening on the day of study treatment.

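### Protocol sections 7 and 8.1 give different rules for when an anticipated symptom is not an adverse event, and 8.1 is silent on vaginal discharge that is worse or longer than it describes

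*Protocol*

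**What the plan says.** Protocol section 7 starts from a broad definition: "An adverse event is any sign, symptom, illness, clinically significant abnormal laboratory value, or other adverse medical event that appears or worsens" during the study, whether or not it is related to the device. It then makes one exemption. Anticipated signs and symptoms, with nausea and cramping as the examples, "which occur in the recovery room will not be considered adverse events unless they occur with greater severity or intensity than anticipated".

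Protocol section 8.1 lists vaginal discharge among the potential risks and adds a note on its usual course: "Vaginal discharge usually happens during the first few days following treatment and may last as long as six weeks". The note describes bloody discharge at first, then a mixed fluid, "followed by a watery discharge that can be substantial at times". It ends with its own rule: "This is an anticipated symptom of the cryotherapy treatment and is not considered an adverse event unless the vaginal discharge suggests infection".

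Three other provisions decide what follows from these rules:

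- **Serious events (section 7).** "An Adverse event is categorized as an SAE if it meets any of the criteria listed below". The same definition says that SAE status does not depend on the severity grade.
- **Unanticipated adverse device effects (section 7).** This category covers serious effects, problems or deaths associated with the device where the effect "was not previously identified in nature, severity, or degree of incidence in the investigational plan or application".
- **Analysis (sections 4.1.2 and 4.1.8.6).** The primary safety endpoint is the proportion of women with a serious event, and its analysis is descriptive. A secondary descriptive analysis covers all adverse events. Section 7 adds summaries by site, severity, relatedness and seriousness. The SAP text deals with effectiveness and gives no adverse event rule.

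**The concern.** The two exemptions differ in setting and in what lifts them. Section 7 has a severity safeguard, and section 8.1 has none. Section 8.1 also takes the exemption out of the recovery room and into the weeks at home, without saying whether the six weeks it mentions are the end of the exemption or only a description.

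Discharge is a symptom that the protocol itself attributes to the treatment. The study has one arm, at up to 20 centers in 3 countries, so there is no control group in which the same recording rule would apply. An abnormal case left out lowers the device's reported rate, and a case counted at one site but not at another distorts the summary by site. If an event must be an adverse event before it can be an SAE, the exemption might also reach the primary safety endpoint.

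**Working it through.** No figure in the plan bears on this, so there is nothing to reproduce. The check is to set the rules side by side and run cases through them.

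**Step 1: the two rules.**

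| Feature | Section 7 exemption | Section 8.1 exemption |
|---|---|---|
| Setting | Recovery room only | After treatment, over a course described as up to six weeks |
| Lifted by unexpected severity or intensity | Yes | Not written |
| Lifted by signs of infection | Not written | Yes |
| Time limit | Implied by the setting | Six weeks described, not stated as a limit |

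**Step 2: four cases of discharge after the recovery room.**

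| Case | Section 7 alone | Section 8.1 |
|---|---|---|
| Within the described course | Adverse event, because the exemption is confined to the recovery room | Exempt |
| Within six weeks, no infection, worse than expected | Adverse event | Exempt on the literal words |
| Beyond six weeks, no infection | Adverse event | Depends on what the first word of the exempting sentence refers to |
| Suggests infection | Adverse event | Adverse event |

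The first case can be settled by letting the specific rule override the general one. The second and third cannot be settled from the text. If that first word refers to the symptom, both are exempt. If it refers to the course just described, discharge beyond six weeks is an adverse event. Discharge worse than described might be one too, but the note's description of intensity is loose and gives a site little to judge against.

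**Step 3: will the third case arise?** All adverse events are collected through Month 12 (Table 3). The Week 2 visit allows 2 more weeks, so it falls in weeks 2 to 4. The next visit is Month 3, with a window of 4 weeks either side. Three months is about 13 weeks, so the window opens at about 13 − 4 = 9 weeks. The Month 3 adverse event query therefore always falls after the six weeks, and any non-infectious discharge still present then meets the unclear rule.

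**Step 4: what is lost.** The mild, moderate and severe grades in section 7 apply to adverse events. Exempt discharge is not graded and does not enter the all-adverse-event analysis in 4.1.8.6.

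**Step 5: serious events.** A high severity grade does not make an SAE. The exemption matters here only if discharge met a seriousness criterion, such as hospitalization, and a site still treated it as the anticipated symptom.

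**Step 6: size.** The documents give no frequency for discharge that is worse or longer than described. The only arithmetic available is a conversion: 242 × 0.01 = 2.42, so each percentage point of women affected is about 2.4 women. How many points apply is unknown.

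**The case against.** A reader might infer that section 8.1 exempts discharge at any severity and for any duration, so that severe or prolonged discharge is never counted. The documents do not support that:

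- Neither limitless severity nor limitless duration is written. The exempting sentence follows a description of an expected course and can be read as confined to it, in which case later discharge returns to the broad definition in section 7.
- Discharge suggesting infection is counted. Vaginal bleeding, endometritis, infection and fever are separate listed risks with no exemption.
- The unanticipated adverse device effect category does not pass through the exemption, so a serious effect beyond what was identified has its own reporting route.
- Parts of section 7 after Table 3, and of section 5.5, are redacted and may hold reporting instructions.

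It can also be said that a specific rule for one after-effect supplements a general rule for the recovery room without contradicting it, and that the consequence is small: the primary safety endpoint counts serious events only, is descriptive, and carries no success criterion.

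Most of this stands, and it limits the point to a gap in wording with a modest effect. It does not close the gap. The narrow reading is available but not stated. Reading 8.1 as the specific rule makes the missing severity clause matter more, because section 7's clause then no longer applies to discharge. The separate listing of vaginal bleeding helps only in part, since the note calls early discharge bloody and draws no line between the two. The device effect route covers serious effects only, and sections 4.1.2 and 4.1.8.6 do not name it as a tabulated category.

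**Conclusion.** The point holds as an inconsistency between two recording rules. Section 7 lifts its exemption for unexpected severity and section 8.1 does not. Section 8.1 also leaves open whether discharge beyond six weeks is an adverse event. On the literal words, non-infectious discharge worse than expected is neither recorded nor graded, and longer-lasting discharge is left to each site's reading.

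Any error in the device's rate is downward. It falls mainly on a secondary descriptive table and reaches SAE classification only in rare cases. Its size cannot be estimated from the documents. The conclusion assumes that the redacted text does not already settle the matter, and that at least some sites would apply 8.1 as worded. The change is worth making because it corrects a stated counting rule in a single-arm safety table at little cost.

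**What to change.** Reconcile the two passages, using terms the protocol already contains:

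- In section 8.1, limit the exemption to discharge that stays within the course the note describes, up to six weeks, and is no more severe or intense than anticipated.
- State that any other discharge, and any discharge suggesting infection, is recorded as an adverse event and given a section 7 severity grade.
- In section 7, add a cross-reference to the 8.1 rule, since the recovery-room limit there otherwise conflicts with it.
- Add a line to the site instructions so that all centers apply one rule.

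This changes how events are recorded, not how women are managed. It does turn a descriptive six weeks into a reporting limit, which the sponsor should confirm is the intended course. The cost is about a sentence in each section, a few more adverse event records and a slightly less favourable adverse event rate.
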